2.2 Study objectives and endpoints

The study objectives and related endpoints see [Table 2-1](#).

Table 2-1 Objectives and related endpoints

Objectives	Endpoints
Primary objectives 
• To demonstrate similar efficacy of GP2017 and US-licensed Humira® in patients with moderate to severe active RA up to Week 12	Primary endpoint 
• DAS28-CRP score change from baseline up to Week 12
Key secondary objective 
• To demonstrate similar efficacy of GP2017 and US-licensed Humira® in patients with moderate to severe active RA until Week 24	Key secondary endpoint 
• Time-weighted averaged change from baseline in DAS28-CRP until Week 24
Other secondary objectives in Study Period 1 
• To demonstrate similar efficacy and to compare safety and immunogenicity of GP2017 and US-licensed Humira® in patients with moderate to severe active RA over 24 weeks of treatment	Other secondary endpoints in Study Period 1 
• Proportion of GP2017 and US-licensed Humira® treated patients achieving EULAR criterion for remission at Week 4, 12, 24• Proportion of GP2017 and US-licensed Humira® treated patients achieving EULAR criterion for good response at Week 4, 12, 24• Proportion of GP2017 and US-licensed Humira® treated patients achieved EULAR moderate response at Week 4, 12, 24• DAS28-CRP and DAS28-ESR changes from baseline in GP2017 and US-licensed Humira® treated patients at Week 2, 4, 24

Objectives	Endpoints
	
• Proportion of GP2017 and US-licensed Humira® treated patients achieving remission according to Boolean definition (TJC (28 joints) ≤1, SJC (28 joints) ≤1, CRP≤1 mg/dl and patient global assessment (PtGA)≤1 on a scale of 1-10 (corresponding to ≤10 on a scale of 1-100) at Week 4, 12, 24• Proportion of GP2017 and US-licensed Humira® treated patients achieving ACR20/50/70 (based on CRP & ESR) responses at Week 4, 12, 24• Health Assessment Questionnaire-Disability Index (HAQ-DI) changes from baseline in GP2017 and US-licensed Humira® treated patients at Week 4, 12 and 24• Proportion of GP2017 and US-licensed Humira® treated patients achieving HAQ-DI score ≤0.5 at Week 4, 12 and 24• Proportion of GP2017 and US-licensed Humira® treated patients with HAQDI score improvement >0.3 at Week 4, 12 and 24• FACIT Fatigue scale changes from baseline in GP2017 and US-licensed Humira® treated patients at Week 4, 12 and 24• CRP and ESR changes from baseline in GP2017 and US-licensed Humira® treated patients over time• Clinical safety of GP2017 and US-licensed Humira® as assessed by changes in vital signs, clinical laboratory parameters and incidence and severity of Adverse Events (AE)• Incidence and severity of injection site reactions (ISRs) in GP2017 and US-licensed Humira® treated patients• Immunogenicity as determined by measuring the rate of anti-drug antibody (ADA) formation against adalimumab in GP2017 and US-licensed Humira® treated patients

Other secondary objectives in Study Period 2

- To evaluate long-term safety, immunogenicity and efficacy of GP2017 up to Week 48 and to investigate the effects of a switch from US-licensed Humira® to the proposed biosimilar GP2017 in patients with at least a moderate response, with respect to efficacy, safety and immunogenicity

Other secondary endpoints in Study Period 2

- Clinical safety in patients treated continuously with GP2017 and in patients treated with GP2017 after switch from US-licensed Humira® as assessed by changes in vital signs, clinical laboratory parameters and incidence and severity of AE
- Incidence and severity of injection site reactions (ISRs) in patients treated continuously with GP2017 and in patients treated with GP2017 after switch from US-licensed Humira®
- Immunogenicity as determined by measuring the incidence of ADA formation against adalimumab in patients treated continuously with GP2017 and in patients treated with GP2017 after switch from US-licensed Humira®

Objectives	Endpoints
	
• Efficacy in patients treated continuously with GP2017 and in patients treated with GP2017 after switch from US-licensed Humira® as assessed by DAS28-CRP, DAS28-ESR score changes from Week 24 at Week 48 and ACR20/50/70 responses at Week 48• Health Assessment Questionnaire-Disability Index (HAQ-DI) changes from Week 24 at Week 48 in patients treated continuously with GP2017 and in patients treated with GP2017 after switch from US-licensed Humira®• Proportion of patients treated continuously with GP2017 and patients treated with GP2017 after switch from US-licensed Humira® achieving HAQ-DI score ≤0.5 at Week 48• Functional Assessment of Chronic Illness Therapy (FACIT) Fatigue scale changes from Week 24 at Week 48 in patients treated continuously with GP2017 and in patients treated with GP2017 after switch from US-licensed Humira®

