### Other secondary objectives

[figure not shown]
#### Study period 1: baseline (randomization) - Week 24

[figure not shown]
- To compare the proportion of GP2017 and US-licensed Humira® treated patients achieving EULAR criterion for remission at Week 4, 12, 24
- To compare the proportion of GP2017 and US-licensed Humira® treated patients achieving EULAR criterion for good response at Week 4, 12, 24
- To compare proportion of GP2017 and US-licensed Humira® treated patients achieved EULAR moderate response at Week 4, 12, 24
- To compare DAS28-CRP and DAS28-ESR changes from baseline in GP2017 and US-licensed Humira® treated patients at Week 2, 4, 24
- To compare the proportion of GP2017 and US-licensed Humira® treated patients achieving remission according to Boolean definition (TJC  $\leq 1$ , SJC  $\leq 1$ , CRP  $\leq 1$  mg/dl and patient global assessment (PtGA)  $\leq 1$ ) at Week 4, 12, 24
- To compare the proportion of GP2017 and US-licensed Humira® treated patients achieving ACR20/50/70 (based on CRP & ESR) responses at Week 4, 12, 24
- To compare Health Assessment Questionnaire-Disability Index (HAQ-DI) changes from baseline in GP2017 and US-licensed Humira® treated patients at Week 4, 12 and 24
- To compare the proportion of GP2017 and US-licensed Humira® treated patients achieving HAQ-DI score  $\leq 0.5$  at Week 4, 12 and 24
- To compare proportion of GP2017 and US-licensed Humira® treated patients with HAQ-DI score improvement  $> 0.3$  at Week 4, 12 and 24
- To compare FACIT Fatigue scale changes from baseline in GP2017 and US-licensed Humira® treated patients at Week 4, 12 and 24
- To compare CRP and ESR changes from baseline in GP2017 and US-licensed Humira® treated patients over time
- To compare clinical safety of GP2017 and US-licensed Humira® as assessed by changes in vital signs, clinical laboratory parameters and incidence and severity of Adverse Events (AE)
- To compare incidence and severity of injection site reactions (ISRs) in GP2017 and US-licensed Humira® treated patients

- To compare immunogenicity as determined by measuring the rate of anti-drug antibody (ADA) formation against adalimumab in GP2017 and US-licensed Humira® treated patients

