### **Study Period 2 (Week 24 - Week 48)**

At Week 24 (Visit 14) all patients with at least moderate DAS28-CRP response, as defined by EULAR response criteria (see [Table 6-3](#)) will continue or will be switched to GP2017. The dosage and frequency will not be changed.

In Study Period 2, all patients will self-administer GP2017 injections. At Week 24 (Visit 14) after appropriate training, patient will self-administer GP2017 under the supervision of qualified study personnel at study site. After being assessed as proficient at self-administration, the patient will receive written IFU for GP2017 and will continue to self-administer GP2017 injections. However, if the unblinded study team member concludes at the Visit 14 (Week 24) that the patient cannot perform self-administration as per study protocol and needs further training the patient should be invited back to the site for further training until deemed proficient.

Patients not achieving at least a moderate response will have their final assessment at Week 24 (as per assessment schedule defined for EoS/ Visit 16) and will not continue in the study.

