2.3.1.4 EULAR response criteria

The EULAR good response, moderate response, and no response based on the DAS28-CRP are defined as follows.

Table 2-2 EULAR response criteria

Improvement in DAS28 from baseline			
Present DAS28	> 1.2	> 0.6 and ≤ 1.2	≤ 0.6
≤ 3.2	good response	moderate response	no response

Improvement in DAS28 from baseline			
Present DAS28	> 1.2	> 0.6 and \leq 1.2	\leq 0.6
> 3.2 to \leq 5.1	moderate response	moderate response	no response
> 5.1 (high)	moderate response	no response	no response

EULAR remission is defined as DAS28-CRP < 2.6.

If the DAS28-CRP is missing then the EULAR response is set to missing. Note that it is a condition of continuation into SP2 that a patient show at least a moderate response based on DAS28-CRP at Week 24 (using Week 22 CRP values).

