4.2 Disposition of patients and protocol deviations

Frequency and percentage of patient's recruitment by region, country, site, and treatment group will be presented.

Disposition of patients includes the number and percentage of patients for the following categories: randomized, completed Week 12, discontinued before Week 12, completed SP1, discontinued during SP1, eligible to enter SP2 (achieving at least a moderate EULAR response assessed by DAS28-CSR at Week 24), entered SP2, completed SP2, discontinued during SP2. The primary reason for discontinuation in SP1/SP2 will be summarized.

A patient who completed the Visit 14 (Week 24) is considered to have completed SP1.

Frequency and percentage of patients having major and minor protocol deviations will be presented by deviation category, treatment group and overall for all patients in FAS. Patient having major and minor protocol deviations will be counted only once under more severe deviation category. Patients who are excluded from each analysis population and protocol deviations will also be listed.

All percentages for the summaries will be based on the number of patients in FASs (SP1 FAS for study period 1 and during the entire study, or, SP2 FAS for study period 2).

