4.6.1.3 Analysis of EULAR over time

The number and proportion of patients achieving EULAR good and moderate response, as well as EULAR remission criteria in DAS28-ESR at weeks 2, 4, 12, 24, 36 and 48 will be summarized and plotted by treatment and visit.

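### EULAR moderate response reported alone is an exclusive middle category with no fixed direction in efficacy; good-or-moderate response should be the comparison beside good response.

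*SAP*

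**What the plan says.** Protocol 2.2 makes the category a between-product objective: "To compare proportion of GP2017 and US-licensed Humira® treated patients achieved EULAR moderate response at Week 4, 12, 24". SAP Table 2-1 turns it into the endpoint "Proportion of GP2017 and US-licensed Humira® treated patients achieved EULAR moderate response at Week 4, 12, 24", next to a separate one: "Proportion of GP2017 and US-licensed Humira® treated patients achieving EULAR criterion for good response at Week 4, 12, 24".

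The definition is in SAP 2.3.1.4: "The EULAR good response, moderate response, and no response based on the DAS28-CRP are defined as follows". Table 2-2 there, like Protocol Table 6-3, puts each patient in exactly one of three cells.

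The planned display is in SAP 4.6.1.3: "The number and proportion of patients achieving EULAR good and moderate response, as well as EULAR remission criteria in DAS28-ESR", summarised and plotted by treatment and visit. That section does not say whether moderate includes good, and it names no combined rate.

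Where the cumulative group is meant, the documents say so. Protocol 5.2 continues "all patients with at least moderate DAS28-CRP response" into Study Period 2, and the disposition table in SAP 4.2 counts patients "achieving at least a moderate EULAR response assessed by DAS28-CSR at Week 24". The natural reading of the endpoint is therefore the exclusive one.

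**The concern.** A proportion used to compare two products should move one way when one of them works less well. An exclusive middle category need not do so. Lower efficacy moves some patients from good to moderate and others from moderate to none, and the net change depends on where the distribution lies relative to the cut-offs. Equal moderate rates then do not show similarity, and a higher rate does not show benefit. The cumulative rate does have a fixed direction, but the efficacy analyses do not list it. What is at stake is whether one listed secondary comparison can be interpreted. The primary conclusion is not at stake.

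**Working it through.** **The plan's own figure.** SAP 2.5.1 gives SD 1.30, margin 0.6, 154 per arm and 246 evaluable (123 per arm).

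- SE = 1.3 × √(2/123) = 0.166, and 0.6/SE = 3.62.
- Power = 2Φ(0.6/SE − z) − 1. With z = 1.645 (90% CI) this is 95.2%; with z = 1.960 (95% CI) it is 90.3%.
- The stated 95% and 90% are reproduced, so the SD, margin and sample size are used below as given.

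**Inputs for the response categories.**

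- From the documents: SD of change 1.3; SD of DAS28-CRP 0.9 to 1.0 (SAP 2.5.2), used as the baseline SD; the screening threshold of 3.2, applied as a truncation of baseline; the scale minimum 0.96 (SAP 2.3.1.2); the cells of Table 2-2.
- Not in the documents, so assumed: baseline mean 4.5, 5.0, 5.5 or 6.0; reference mean improvement 1.5, 1.8, 2.0, 2.2 or 2.5; correlation of baseline with improvement 0 or 0.4.
- Scenarios: 4 baseline means × 5 improvements × 2 correlations × 2 baseline SDs = 80, with 400,000 simulated patients each. The worse product has 0.6 less mean improvement.

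**Formula.** With G, M and N the proportions good, moderate and none, M = 1 − G − N. The change in M is therefore the loss from good minus the gain in none. The change in G + M is minus the gain in none, so it can only fall as non-response rises.

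**Examples** (baseline SD 1.0, correlation 0; reference → worse product, %):

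| Baseline mean | Mean improvement | Good | Moderate | None | Good or moderate |
|---|---|---|---|---|---|
| 4.5 | 2.0 → 1.4 | 59.1 → 42.6 | 25.8 → 29.2 | 15.1 → 28.2 | 84.9 → 71.8 |
| 5.0 | 2.0 → 1.4 | 50.9 → 35.4 | 32.9 → 34.9 | 16.2 → 29.7 | 83.8 → 70.3 |
| 5.5 | 2.0 → 1.4 | 41.2 → 27.1 | 40.8 → 40.7 | 18.1 → 32.2 | 81.9 → 67.8 |
| 6.0 | 2.0 → 1.4 | 30.9 → 19.0 | 48.7 → 45.7 | 20.4 → 35.3 | 79.6 → 64.7 |
| 6.0 | 1.5 → 0.9 | 20.8 → 11.6 | 46.7 → 38.5 | 32.6 → 49.9 | 67.4 → 50.1 |

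At baseline 5.0 good loses 15.5 points and none gains 13.5, so moderate rises by 2.0. At baseline 6.0 with improvement 2.0, good loses 11.9 and none gains 14.9, so moderate falls by 3.0. The true deficit is the same in both.

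**All 80 scenarios.**

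- Moderate alone: up by at least 1 point in 45, within 1 point in 12, down by at least 1 point in 23; range −10.3 to +9.8 points.
- Good or moderate: down in all 80, by 8.9 to 18.7 points.
- Good: down in all 80, by 8.4 to 19.6 points.

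**Where the sign turns.** With baseline SD 1.0, moderate stops falling and starts rising at a reference improvement of about 1.45–1.6 (baseline 4.5), 1.65–1.8 (5.0), 1.9–2.05 (5.5) and 2.2–2.3 (6.0). An SD of change of 1.5, the Week 24 figure in SAP 2.5.2, moves these points by at most 0.05.

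**Observed rates with 123 per arm.** The chance that the worse product's observed rate equals or exceeds the reference is Φ(d/SE_d), where d is worse minus reference and SE_d = √[p₁(1−p₁)/123 + p₂(1−p₂)/123]. At baseline 5.0 with improvement 2.0, moderate gives d = 0.020 and SE_d = 0.060, so 63%. Over the 80 scenarios the chance is 5% to 95% for moderate alone, at most 1.5% for good or moderate, and at most 2.5% for good.

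**The case against.** The strongest reply is that nothing is lost. SAP 2.1.2 puts the categories on a common denominator, and 4.6.1.3 shows good and moderate by treatment and visit. The categories are exclusive, so a reader can add the two rows, and the good row alone would expose a deficit of 0.6. The EULAR rates carry no test, interval, margin or success rule; equivalence rests on DAS28-CRP change at Week 12, with its time-weighted average as key secondary. All of this stands and keeps the point minor. It does not make the moderate row interpretable as the comparison that Protocol 2.2 announces.

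A reader might go further and infer that the moderate rate always stays flat or rises for a worse product. It does not: it falls when the reference improvement is small relative to baseline, as in 23 of the 80 scenarios. If improvement is smaller at Week 4 than later, a fall is more likely there, so the direction could differ between visits.

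A reader might also infer that the plan never counts the cumulative response. SAP 4.2 does count it at Week 24, for disposition. The continuation decision behind that table uses Week 22 CRP, whereas Week 24 efficacy uses Week 24 CRP (SAP 2.3.1.2), and the table does not cover Weeks 4 or 12. The gap is therefore in the efficacy analyses only.

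**Conclusion.** The point holds in limited form. Under Table 2-2 the proportion with moderate response alone is not monotone in efficacy: for a product worse by the full margin it can rise, stay flat or fall. The counts and ranges rest on the assumed baseline means, improvements and correlations and on a normal model, so 57 of 80 is not a probability for this trial. The conclusion that the direction is not fixed follows from the category structure, and the fall in good-or-moderate holds throughout the assumed range. The consequence is confined to one descriptive secondary endpoint. A reader might infer that the equivalence conclusion is exposed; the documents do not support that, because no decision uses this rate.

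One inconsistency belongs with it. SAP 2.3.1.4 defines EULAR response on DAS28-CRP and Protocol 9.5.2 plans the EULAR rates on DAS28-CRP, but SAP 4.6.1.3 names DAS28-ESR. It is unclear whether that applies to remission only or to all the categories.

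**What to change.** 1. In SAP Table 2-1 and 4.6.1.3, make the comparison at least moderate (good or moderate) EULAR response at Weeks 4, 12 and 24, beside good response.
2. Keep the three-category distribution as description, and state that moderate there excludes good.
3. Record the change in SAP Section 3, since the protocol lists moderate response as a secondary objective. If the database is already locked, the SAP Introduction requires an addendum and an explanation in the study report.
4. Reconcile the DAS28-ESR in 4.6.1.3 with the DAS28-CRP definition in 2.3.1.4.

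The cost is one derived variable, one table row per visit and a short entry in Section 3. No new data are needed, and the sample size and primary analysis do not change.

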2.3 Assessments

2.3.1 Efficacy assessments

2.3.1.1 Joint counts (TJC28, SJC28, TJC68 and SJC66)

A joint which is missing consistently throughout the study will be imputed as “not swollen” and “not tender”. This is the most commonly (76%) used procedure for imputation in publications of RA trials ([Ibrahim et al, 2016](#)).

Most joints will not have swelling or tenderness and hence a non-swelling, non-tender is the most plausible value to use for imputation. In most cases the joint cannot be assessed for a specific reason, e.g. surgery or joint replacement in which cases it is clinically appropriate to consider these joints as not having tenderness or swelling. Since we are primarily interested in the change in the DAS28 from baseline then the exact method of imputation will not have a substantial impact. With this in mind it is important that a joint has to be missing consistently throughout the study when this imputation method is applied. So for example, a joint replacement or surgery conducted during the trial would be considered a sufficient reason to exclude the patient from the PPS, although the patient would still be included within the FAS analysis.

The effect of non-swelling, non-tender imputation is that the DAS28 will be calculated with the lowest possible score. Hence, it is assured that patients that meet the inclusion criterion of

DAS28-CRP ≥ 3.2 at screening using this method of imputation would have met the inclusion criterion regardless of the value of the unassessed joints.

However, for this analysis to be meaningful it is recognized that there must be a minimum number of joints assessed beyond which the joint count will become unreliable. Hence it was decided that if more than two of the joints are missing then the 28-joint counts (TJC28 and SJC28) cannot be calculated. The full tenderness joint counts TJC68 will not be calculated if 4 or more joint counts are missing or if the TJC28 cannot be calculated. The full swelling joint counts SJC66 will not be calculated if 4 or more joint counts are missing or if the SJC28 cannot be calculated.

[figure not shown]
The number of missing joints at baseline will be presented in the baseline table and also be listed.

The following joints (see [Figure 2-1](#)) are included into the 28-joint count:

- Shoulder (left and right) – 2 joints
- Elbow (left and right) – 2 joints
- Wrist (left and right) – 2 joints
- MCP I to V (left and right) – 10 joints
- PIP I to V (left and right) – i.e. including thumbs – 10 joints
- Knee (left and right) – 2 joints

Note that distal inter-phalangeal joints are not included.

Figure 2-1 28-Joint count

2.3.1.2 DAS28-CRP

The disease activity score (DAS) is a combined index to measure the disease activity in patients with RA. The DAS28-CRP is calculated as

$$\text{DAS28-CRP} = 0.56 \times \sqrt{(\text{TJC28})} + 0.28 \times \sqrt{(\text{SJC28})} + 0.36 \times \ln(\text{CRP}+1) + 0.014 \times \text{PtGA} + 0.96$$

With TJC28, SJC28 measured as described in Section 2.3.1.1, the C-reactive protein (CRP) measured in mg/L units, and the patient's global assessment of disease activity (PtGA) measured in mm indicated by marking a 100 mm line between very good and very bad. For CRP values below the limit of detection (<1 mg/L) value of zero will be used in the DAS28-CRP calculation.

The DAS28-CRP provides a number on a scale from 0.96 to 10 indicating the current activity of the RA of the patient.

TJC28 and SJC28 for patients with partially missing joint counts can be imputed using imputation defined in Section 2.3.1.1. DAS28-CRP will not be imputed if any of the components (TJC28, SJC28, CRP or PtGA) are missing.

Due to several days needed to obtain the CRP results from central laboratory, the decision to continue patients in the study after Week 24 was to be made based on Week 24 DAS28 parameters and the CRP value from Week 22. However for the statistical analysis the DAS28-CRP score at Week 24 will be calculated based on the Week 24 CRP value provided by the central laboratory. The analysis date for DAS28-CRP will be the date of the nominal visit.

2.3.1.3 DAS28-ESR

The DAS28-ESR is calculated as

$$\text{DAS28-ESR} = 0.56 \times \sqrt{(\text{TJC28})} + 0.28 \times \sqrt{(\text{SJC28})} + 0.70 \times \ln(\text{ESR}) + 0.014 \times \text{PtGA}$$

With TJC28, SJC28 measured as described in Section 2.3.1.1, the ESR measured using mm/h units and PtGA measured in mm. ESR in adults is expected to be ≥ 1 mm/h, however in some cases the lab kit can record a zero value. In these cases the value of 1 mm/h will be used in the DAS28-ESR calculations above to make the formula calculable. The analysis date for DAS28-ESR will be the date of the nominal visit.

The DAS28-ESR provides a number on a scale from 0 to 10 indicating the current activity of the RA of the patient. The DAS28-ESR will be missing if any of the TJC28, SJC28, ESR or PtGA are missing.

2.3.1.4 EULAR response criteria

The EULAR good response, moderate response, and no response based on the DAS28-CRP are defined as follows.

Table 2-2 EULAR response criteria

Improvement in DAS28 from baseline			
Present DAS28	> 1.2	> 0.6 and ≤ 1.2	≤ 0.6
≤ 3.2	good response	moderate response	no response

Improvement in DAS28 from baseline			
Present DAS28	> 1.2	> 0.6 and \leq 1.2	\leq 0.6
> 3.2 to \leq 5.1	moderate response	moderate response	no response
> 5.1 (high)	moderate response	no response	no response

EULAR remission is defined as DAS28-CRP < 2.6.

If the DAS28-CRP is missing then the EULAR response is set to missing. Note that it is a condition of continuation into SP2 that a patient show at least a moderate response based on DAS28-CRP at Week 24 (using Week 22 CRP values).

